Treating Where it Hurts: A randomized blinded clinical trial of local estrogen to the vulvar vestibule for dyspareunia in postmenopausal women

NCT03240081

13MAR2019

Principal Investigator: [name], MPH

eIRB #: 16770

1. Protocol Title

Treating Where it Hurts: A randomized blinded clinical trial of local estrogen to the vulvar vestibule for dyspareunia in postmenopausal women

2. Objectives

Purpose:

To perform a pilot study to evaluate the efficacy and safety of local estrogen therapy applied to the vulvar vestibule in a cohort of postmenopausal women with moderate or severe dyspareunia, and to examine the microscopic features of this condition before and after local estrogen therapy.

Primary goals:

- 1. To compare serum levels of β -estradiol before and during paired dosing of the hormone to the vulvar vestibule nightly.
- 2. To assess the comparative treatment efficacy of two strengths of β -estradiol dosed at an increased frequency to the vulvar vestibule.
- 3. To assess and characterize the microscopic features of tender vulvar vestibule tissues in postmenopausal women who have moderate to severe dyspareunia acquired since menopause.
- 4. To assess whether β-estradiol cream applied nightly for three months to the vulvar vestibule normalizes the microscopic profile of vestibule findings in parallel with correction of dyspareunia.

Hypotheses:

- 1. Topical estrogen to the vulvar vestibule is safe
 - a. β-estradiol serum levels associated with nightly estrogen applications to the vulvar vestibule will not be significantly different than levels published in studies of vaginal applications.
- 2. This condition is a form of vestibulodynia and will regress with topical estrogen therapy
 - a. For postmenopausal women with significant coital pain, vestibule biopsies will show neural hyperplasia and an infiltrate of lymphocytes, hallmarks of localized provoked vulvodynia, and doses of topical β -estradiol will be effective when applied to the zone of tenderness, the vestibule.
- 3. Nightly therapy to the vestibule will be more efficacious than published results of standard semiweekly vaginal therapy.
 - a. Nightly therapy will effect a correction of moderate/severe dyspareunia in greater than 62% of subjects, a published rate of correction using the standard treatment frequency to the vagina.

Primary endpoints:

- 1. Serum levels of β -estradiol before and during treatment with two strengths of cream applied locally to the vestibule.

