 - O Diary questions include pain scoring of either a Tampon Test (a validated test used to assess vestibular tenderness), or a sexual penetration encounter

Visit 3 (12 hour blood draw +/- 60 minutes)

• Blood sample collection for serum β-estradiol [12 hours after the initial study drug dose (8 or 9am after an initial dosing at 8 or 9pm the evening before)]

Visit 4 (week 4 +/- 3 days)

- Update to medical and medication history
- Review of possible symptoms associated with study drug
- Collection and review of diary, additional pages dispensed as needed
- Pelvic examination to assess genital atrophy and vestibule tenderness
- Blood sample collection for serum β-estradiol
- Completion of questionnaire, VPAQ #2

Visit 5 (week 8 +/- 3 days) – telephone or email contact only

- Update to medical and medication history
- Review of possible symptoms associated with study drug
- Review of diary

Visit 6 (week 12 +/- 3 days)

- Update to medical and medication history
- Review of possible symptoms associated with study drug
- Collection and review of diary
- Pelvic examination to assess genital atrophy and vestibule tenderness
- Collection of swabs from the vestibule and from the vaginal side walls for later analysis of the microbiome composition.
- Repeat transvaginal ultrasound to assess endometrial stripe thickness
- Blood sample collection for serum β-estradiol
- Completion of questionnaires: VPAQ #3 and LUTS questionnaire
- Remaining study medication collected from participant by study staff
- Repeat vulvar biopsy (for those subjects enrolled in the sub-study)

Visit 7 (follow-up)

• Subjects will be contacted by phone, mail or email 4 months after study completion to ask the status of their dyspareunia and estrogen regimens and to administer follow-up questionnaires (VPAQ modified + LUTS questionnaire).

Long-term follow up

Study staff may request permission to contact subjects by telephone or email for up to 5 years to ask the status of their pain and any medication they are using to treat their pain.

Duration of Participation:

The duration of active participation will be 12 weeks and limited further data will be obtained from a phone call, mail, or electronic communication 7 months after enrollment into the study. Participants may be asked to allow additional follow-up contact for up to 5 years after their last study visit.

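### Serum estradiol is timed to dosing only at Visit 3; at Visits 4 and 6 the time since application is neither fixed nor stated to be recorded

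*Combined protocol and SAP*

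**What the plan says.** Section 2 makes serum estradiol the first primary goal ("To compare serum levels of β -estradiol before and during paired dosing of the hormone to the vulvar vestibule nightly") and the first primary endpoint (levels "before and during treatment with two strengths of cream applied locally to the vestibule"). Hypothesis 1a is that levels "will not be significantly different than levels published in studies of vaginal applications".

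Section 9 schedules one draw before treatment, at Visit 1, and three during it:

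- **Visit 3:** "Visit 3 (12 hour blood draw +/- 60 minutes"), with the clock times spelled out: "12 hours after the initial study drug dose (8 or 9am after an initial dosing at 8 or 9pm the evening before").
- **Visit 4:** "Visit 4 (week 4 +/- 3 days"), with the entry "Blood sample collection for serum β-estradiol" and nothing on time of day or hours since application.
- **Visit 6:** "Visit 6 (week 12 +/- 3 days"), with the same untimed entry.

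Section 10 asks for nightly application and a diary of applications. It does not mention the time of application. Section 12 contains no analysis of estradiol, so nothing there adjusts for time since dose.

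**The concern.** The protocol treats time since application as worth controlling after the first dose, to within an hour. It then drops that control for the only samples taken under repeated nightly use, which is the exposure the study is about. Section 5 says that absorption from this site has not been studied, and Section 3 offers measuring it as a novelty of the trial.

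Two readings of the data depend on timing. The first is the change from Visit 3 to Visits 4 and 6, which a reader would take as evidence for or against accumulation. The second is the comparison with published vaginal levels. If hours since application differ between women and visits and are not recorded, neither can be separated from sampling time, and the missing times cannot be reliably recovered later.

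**Working it through.** **1. The plan's own window.** From the Visit 3 clock times: 8pm to 8am is 12 h, 8pm to 9am is 13 h, 9pm to 8am is 11 h, and 9pm to 9am is 12 h. The range of 11 to 13 h matches 12 h ± 60 min, so the Visit 3 rule is consistent with itself.

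**2. What Visits 4 and 6 allow.** The 8 or 9pm clock time applies only to the first dose; later doses are just nightly. Assumption (not in the documents): application between 8pm and midnight, and clinic draws between 8am and 5pm. The shortest interval is midnight to 8am, 8 h. The longest is 8pm to 5pm, 21 h. The interval can therefore be shorter or longer than 12 h. Examples: 11pm to 8am is 9 h, 9pm to 1pm is 16 h, and 9pm to 5pm is 20 h.

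**3. What that could do to a reading.** Assumptions for illustration (none from the documents): the rise above baseline declines exponentially from one compartment with half-life h, doses are 24 h apart, and steady state has been reached. Relative to the 12-hour rise after the first dose, a steady-state draw at t hours reads

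R(t) = 0.5^((t − 12)/h) ÷ (1 − 0.5^(24/h)).

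The divisor is the accumulation term:

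- h = 4: 1 − 1/64 = 0.984
- h = 8: 1 − 1/8 = 0.875
- h = 12: 1 − 1/4 = 0.75

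| Draw at | h = 4 | h = 8 | h = 12 |
|---|---|---|---|
| 9 h | 1.682/0.984 = 171% | 1.297/0.875 = 148% | 1.189/0.75 = 159% |
| 12 h | 1/0.984 = 102% | 1/0.875 = 114% | 1/0.75 = 133% |
| 16 h | 0.500/0.984 = 51% | 0.707/0.875 = 81% | 0.794/0.75 = 106% |
| 20 h | 0.250/0.984 = 25% | 0.500/0.875 = 57% | 0.630/0.75 = 84% |

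The 9-hour figure is not monotone in h: it dips to about 148% between the two ends.

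**4. What the Visit 3 rule would remove.** For one half-life, the ratio between an early and a late draw is 2^(Δt/h). From 9 to 20 h (Δt = 11) it is 2^(11/4) = 6.7-fold at h = 4 and 2^(11/12) = 1.9-fold at h = 12. Within 11 to 13 h (Δt = 2) it is 2^(2/4) = 1.41-fold and 2^(2/12) = 1.12-fold. At a fixed 12 h, what remains in the table (102% to 133%) is accumulation alone, which is what the comparison with Visit 3 should show.

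**The case against.** Several points on the other side stand.

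- **Some comparisons are little affected.** The Visit 1 sample precedes dosing and has no post-dose time. Visits 4 and 6 share one rule, so between them loose timing adds variability with no built-in shift. The two strengths are randomized and blinded, so that comparison mainly gains noise. It would be too broad to call the levels not comparable across visits.
- **First dose against repeated dose is not a stated goal.** The goal is before against during treatment. Even so, the during-treatment levels are the endpoint, and their spread depends on timing.
- **The rise may be small.** Section 15 says that with deep vaginal use at the same dose, most women's levels stay as in non-users. A percentage of a near-zero rise matters little. The documents give no absolute level for the vestibule, so this cannot be settled from them.
- **The diary may capture clock time.** Its form is not in the documents. They do not say that it does.
- **This is a pilot, and safety also rests on endometrial thickness,** a separate primary endpoint that does not depend on draw time.

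A reader might go further and infer that the Visit 4 and 6 draws come late, read low, and so favour the safety hypothesis. The documents do not support that. Nothing places those draws beyond 12 hours, because the evening clock time is given for the first dose only. Accumulation also works the other way: with a 12-hour half-life, a 16-hour draw would be 79% of the 12-hour rise after the same single dose, but about 106% of the Visit 3 rise under nightly dosing. The sampling times of the published vaginal studies are not given either, so no direction can be claimed for that comparison.

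**Conclusion.** The gap is real and affects a primary endpoint. Only one of the three on-treatment estradiol draws is timed to dosing, and the untimed two are the only ones under repeated use. The consequence is avoidable variability in on-treatment levels, plus timing mixed with accumulation in the comparison of Visit 3 with Visits 4 and 6 and in the comparison with published data. The direction of any shift is unknown.

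The illustrative size, from about 25% to 171% of the Visit 3 rise for draws at 9 to 20 hours, rests on an assumed half-life of 4 to 12 hours, one-compartment decline, and assumed application and clinic hours. It shows that timing could matter; it does not estimate what will happen. The absence of a timing rule comes directly from the text and needs none of these assumptions.

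**What to change.** In Section 9, at Visits 4 and 6, draw estradiol 12 hours ± 60 minutes after the previous evening's application, as at Visit 3. Record the clock time of that application and of the draw. Flag samples outside the window and repeat the estradiol analysis without them; Section 12 should say so when it sets out that analysis. If a draw in the window is not feasible for some women, the two recorded times still allow adjustment or a sensitivity analysis.

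The cost is morning appointments at two existing visits, some loss of scheduling freedom, and two data fields. No extra visit or sample is needed, and dosing does not change.

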- 2. Measurements of endometrial thicknesses in subjects with a uterus at study end, comparing results to baseline measurements.
- 3. Changes in tissue lymphocyte densities and neuronal hyperplasia comparing baseline to study end.
- 4. Levels of dyspareunia measured by the Numerical Rating Scale (NRS) during regimens of nightly estradiol therapy applied to the vulvar vestibule, determining how soon and how uniformly this schedule corrects painful penetration in study subjects.

Secondary endpoints:

- 1. Pain descriptors as measured by the modified Vulvar Pain Assessment Questionnaire—screen (VPAQ-screen) (Dargie, 2016)
- 2. Sexual function evaluated using the validated but modified VPAQ-Screen.
- 3. Sexual distress as measured by the (VPAQ-Screen).
- 4. Lower Urinary Tract symptoms (LUTS) of menopause as measured by a set of validated questions.
- 5. Vestibular tenderness as measured clinically by the cotton swab touch test and the lidocaine test.
- 6. Vaginal and vestibular atrophy as measured by visual examination and pH of the vaginal secretions.
- 7. Characterization of the urogenital microbiome via swabs collected from the vestibule and vagina.

3. Background

Pain with sex is a common problem experienced by women after the age of menopause, and it is commonly termed "vulvovaginal atrophy" or "vaginal dryness" by most clinicians (ACOG, 2008). Genitourinary Syndrome of Menopause (GSM) is the new term put forth by two professional societies (Portman, 2014). Vulvar complaints develop in association with loss of ovarian estrogens, and the prevalence of sexual pain in women over 50 is 50% (ACOG, 2008). Symptoms are chronic and tend to worsen over time (Gass, 2013). The relationship of vulvar symptoms to sexual difficulties is well established (Simon, 2014). However, the research into this problem is variable in its focus, and there are many gaps.

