A sub-study of patients will receive vulvar biopsies at baseline and again after the 3-month intervention. A total of 20 paired biopsies (one at baseline and one after the 3-month intervention) will complete this substudy. The number has been estimated using a power analysis based on our previous histopathologic findings (see section 12). Subjects completing both biopsies will be remunerated with \$100. If a subject only completes the baseline biopsy she will not count toward the total as the before and after intervention analysis of the biopsy samples is critical. As such, more than 20 women may enroll in the sub-study, but if any participants discontinue prior to the post-intervention biopsy they will be replaced so a total of 20 paired biopsies will be collected.

Reference patients will be 5 women who are not using estrogen supplements and do not have dyspareunia. They will be recruited from an OHSU urogynecology study of postmenopausal women who have urinary complaints and control women who do not. Among those screened or who have finished the study, we anticipate being able to approach women who are not using estrogen products but who have no urinary complaints and no dyspareunia. We would ask them to fill out the entry questionnaire and have a 4mm mucosal biopsy in the right or left vestibule adjacent to a Bartholin's duct orifice. This is the equivalent location of worst tenderness in women with localized provoked vestibulodynia of postmenopause. Subjects who agree to a biopsy will be remunerated with \$100.

Inclusion and Exclusion Criteria

Potential subjects will first be screened during a phone conversation with the Women's Health Research Unit (WHRU) recruitment coordinator or study staff (see phone screen form). After pre-screening eligibility is confirmed, if subjects want to screen for study participation they will be scheduled to be seen in the WHRU clinic with the study coordinator and study clinician.

In the event of screen failure, data collected by phone and at screening will be retained for separate analysis.

Inclusion Criteria

- 1. Postmenopausal women aged at least 40 years old.
- 2. Postmenopausal, defined by at least one of the following:
 - i. Amenorrhea ≥1 year in women > age 50 with a previously functioning uterus and presence of 1 ovary
 - ii. Bilateral oophorectomy
 - iii. FSH >30 in women with at least 1 ovary who are age 40-50 with >1 year amenorrhea

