Fifty women who are postmenopausal, have moderate or severe entry dyspareunia and meet Friedrich's criteria for vestibulodynia will be recruited into the study. We are assuming a baseline pain score of 70 ± 21.5 (mean \pm std) from a previously reported study of a mixed group of treated and untreated postmenopausal patients with dyspareunia, (Kao, 2012), and we assume a 30% treatment effect after four weeks with the lower-dose intervention drug. A sample size of 50, divided into two arms, allowing for a 10% drop out rate in each of two arms, will achieve >85% power to detect at least 20 points mean difference in dyspareunia pain scoring between the two intervention drug strengths at 4 weeks, with an alpha level of 0.05 for two-sample t-test.

The tissue biopsy sub-group will be 10 subjects from each intervention arm (n=20), and using a one-sided exact test with alpha level of 0.05, this number of subjects will achieve 80% power to detect a difference of 15.6% in inflammation, assuming the baseline proportion of moderate or strong inflammation is 95%. (Leclair, 2013). Patients' biopsies at 3 months will be compared to their baseline biopsy.

To establish a reference group of biopsy specimens, we wish to seek out 5 subjects to fulfill the exploratory aim of assessing the histologic profile of vestibule tissues in postmenopausal women who are not on estrogen and do not have penetrative pain. The prevalence of this type of patient has not been established. We would expect them to have atrophy but no vestibular inflammation or neural hyperplasia. They will not technically be "controls" for purposes of this study. As there are no published studies analyzing the histologic character of the vestibule in such women, the small exploratory number (n=5) does not allow a power analysis. We will recruit these subjects with the help of our Urogynecology colleagues who are doing a study on the vaginal/bladder microbiome and are screening postmenopausal patients.

Swabs with material for microbiome analysis will be analyzed with the help of the Urogyn bioinformatics specialist using QIIME bioinformatics software.

13. Privacy, Confidentiality, and Data Security

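### The biopsy sub-study's stated 80% power is not reached by any exact 5% test tried at n=20; the closest reading gives 61%

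*Combined protocol and SAP*

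**What the plan says.** Section 12 (Data Analysis) plans 10 biopsied women per arm, 20 in all. Its claim is that "this number of subjects will achieve 80% power to detect a difference of 15.6% in inflammation". The method is given as "using a one-sided exact test with alpha level of 0.05". The starting point is stated separately, as "assuming the baseline proportion of moderate or strong inflammation is 95" per cent. The comparison itself is then described: "Patients' biopsies at 3 months will be compared to their baseline biopsy".

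Section 5 (Number of Subjects) rests the 20 pairs on this calculation: "The number has been estimated using a power analysis based on our previous histopathologic findings (see section 12"). It adds that a woman with only a baseline biopsy is replaced, because "she will not count toward the total as the before and after intervention analysis of the biopsy samples is critical". All 20 analysed women therefore have both biopsies, and no dropout allowance enters the power.

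The documents do not name the exact test, and they do not say whether 15.6% is an absolute or a relative difference.

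**The concern.** With 20 women and a proportion near 95%, an exact test can use only a few distinct alpha levels, so its power is often well below what a smooth approximation suggests. The 80% therefore needed checking.

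The stated power implies a 20% chance of missing a 15.6-point drop in moderate or strong inflammation. If the true chance is much higher, a null histology result could be over-read as evidence against the hypothesis in section 2 that the condition regresses with topical estrogen. This sentence is also the statistical basis that section 5 gives for the number of paired biopsies.

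The power statement concerns graded inflammation only. Primary endpoint 3 in section 2 is worded differently: "Changes in tissue lymphocyte densities and neuronal hyperplasia comparing baseline to study end". The calculation does not establish power for that endpoint in either direction.

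**Working it through.** **Inputs (section 12; completeness of pairs from section 5).** n = 20; one-sided alpha = 0.05; baseline p0 = 0.95; difference 15.6%. If absolute, p1 = 0.95 − 0.156 = 0.794. If relative, p1 = 0.95 × (1 − 0.156) = 0.8018. X is the number of the 20 women still moderately or strongly inflamed at 3 months.

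**1. Where the stated figure can be reproduced.** One-sample normal approximation without continuity correction:

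- Power = Φ[(d − 1.645·√(p0(1−p0)/n)) / √(p1(1−p1)/n)].
- √(0.95×0.05/20) = 0.0487 and √(0.794×0.206/20) = 0.0904.
- (0.156 − 1.645×0.0487)/0.0904 = 0.839, and Φ(0.839) = 0.799.
- Solving for 80% power gives d = 15.63 points.

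Both stated numbers are matched. The rule rejects when X is below 20 × (0.95 − 1.645×0.0487) = 17.4, that is, at 17 or fewer. Its true alpha is given in step 2.

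**2. Closest exact reading: one-sample binomial against a fixed 95%.**

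| Reject if | Actual alpha, p = 0.95 | Power, p1 = 0.794 |
|---|---|---|
| X ≤ 16 | 0.0159 | 0.614 |
| X ≤ 17 | 0.0755 | 0.812 |

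Only X ≤ 16 is a 5% test, so the power is 61.4%. The variations are:

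- Relative reading (p1 = 0.8018): P(X ≤ 16) = 0.581.
- 95% as a rounded value between 94.5% and 95.5%, with a 15.6-point drop: 0.635 to 0.593.
- Drop detectable with 80% power: P(X ≤ 16) reaches 0.80 at p1 = 0.741, a drop of 20.9 points.

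**3. Ceiling for any 5% test on this reading.** The most powerful test rejects at X ≤ 16, and at X = 17 with probability (0.05 − 0.0159)/(0.0755 − 0.0159) = 0.572. Its power is 0.614 + 0.572 × (0.812 − 0.614) = 0.727, or 0.699 on the relative reading. Neither reaches 80%.

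**4. Paired reading, dichotomised grade, 20 pairs.** The documents give no rate of reverse changes (not inflamed at baseline, inflamed at 3 months), so 0%, 3% and 5% are assumed. With no reverse changes, exact conditional McNemar needs at least 5 improvers, since 0.5⁴ = 0.0625 and 0.5⁵ = 0.031. The power is then P(Binomial(20, 0.156) ≥ 5) = 0.191.

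| Reverse changes | 0% | 3% | 5% |
|---|---|---|---|
| Conditional McNemar, 15.6-point net drop | 0.191 | 0.201 | 0.197 |
| Unconditional exact McNemar | 0.381 | 0.349 | 0.322 |
| Unconditional, null restricted to reverse rates ≤ 5% | 0.624 | 0.520 | 0.466 |
| Net drop for 80% power (conditional) | 31.3 points | 37.1 points | 40.3 points |
| Conditional power, 40-point net drop | 0.949 | 0.848 | 0.794 |

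**5. Unpaired 20 v 20, 0.95 v 0.794.** One-sided Fisher 0.232; Boschloo 0.323; unconditional pooled-z test 0.392.

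**6. Large effects.** If 70% remain inflamed, the one-sample test of step 2 has P(X ≤ 16) = 0.893.

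**The case against.** - **The test is unnamed, so any particular figure depends on the reader's choice.** This is true, and it is why the conclusion is limited to the tests tried. On the one-sample reading, however, the 73% ceiling holds for every valid 5% test.
- **The 20% McNemar figure is a harsh choice.** The conditional test is conservative with few discordant pairs, and with a 95% baseline reverse changes cannot exceed about 5%. An exact paired test that uses that bound reaches 47–62%. This stands: the paired power is a range of about 20% to 62%, not a single figure. The whole range is below 80%.
- **Grades or densities could be analysed without dichotomising, with different power.** This also stands, but the plan's own calculation uses a proportion.
- **The 95% comes from a cited study that is not available here, and the cut-off is sensitive to it.** With a null of 96%, X ≤ 17 becomes a valid 5% cut-off (alpha 0.044), but power for a 15.6-point drop is still 78%. The conclusion does not change.
- **This is an optional sub-study of a pilot, and nothing operational follows.** This is fair and limits the severity. It does not make the stated power correct, and section 5 relies on it.

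**Conclusion.** The concern holds: 80% power is wrong as written for an exact one-sided 5% test with 20 women. On the closest reading, a fixed 95% and an absolute 15.6-point drop, power is 61% (58% if relative), with a ceiling of 73%. The chance of missing the stated drop is 39%, not 20%. The drop detectable with 80% power is about 21 points, not 15.6.

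A test against a fixed 95% does not make the within-woman comparison that the plan describes. For a 15.6-point net drop, exact paired tests on the dichotomised grade give about 20% (conditional McNemar) to 62% (the most favourable version tried), assuming reverse changes of 0–5%.

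The likeliest explanation is a normal approximation labelled as exact. That is an inference, and the error does not depend on it.

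The consequence is moderate. Twenty pairs remain adequate for large drops, and what needs correcting is the power statement. It should be fixed.

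**What to change.** In section 12:

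1. Name the exact test that will compare each woman's 3-month biopsy with her baseline, and say whether 15.6% is absolute or relative. Check whether the 80% came from a normal approximation. If it did, the figure cannot be kept under the exact-test label.
2. Replace the 80% with that test's power at 20 pairs:
   - **One-sample exact binomial against a fixed 95%:** 61% for a 15.6-point drop; 80% for about 21 points.
   - **Exact one-sided McNemar on the dichotomised grade:** about 20% for a 15.6-point net drop; 80% for roughly 31 points or more. State the assumed rate of reverse changes.
   - **Another exact paired test:** its own power, with the same assumption stated.

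The cost is wording and a less favourable stated power. No patients, biopsies or visits are added.

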Another research issue relates to the historical focus by clinicians and researchers on atrophy as the causative process that explains coital discomfort and pain after menopause. Our clinical experience leads us to a different hypothesis because of decades as experts in dyspareunia care and vulvar health. Our overarching hypothesis is that postmenopausal dyspareunia is a localized pain condition of the vestibule and is caused by neural hyperplasia such as is found in the chronic condition of localized provoked vulvodynia. This condition can be caused by low or absent circulating estrogen, and therefore in postmenopause it occurs in parallel with the tissue thinning that characterizes atrophy. However, whereas atrophy occurs in all genital tissues from uterus to vulva, the allodynia of neural hyperplasia is localized to the vulvar vestibule. Our research group has published work demonstrating neural hyperplasia in the vestibular tissues of postmenopausal women who still had dyspareunia despite use of systemic and/or local vaginal estrogens (Leclair, 2013). This project will explore the historic paradigm of atrophy as the cause of dyspareunia. The standard therapeutic dosage and timing regimen for local estrogen was derived from previous studies that used atrophy rather than pain as the primary endpoint. We will analyze tissue biopsies from the vulvar vestibule before and after the intervention

of vestibule estrogen, comparing neural hyperplasia, lymphocyte and mast cell infiltrate densities, which are all hallmarks of localized provoked vestibulodynia. (Leclair, 2013)

Vaginal atrophy has a well-established set of findings as defining features. These include the maturation index, which is a microscopic evaluation of squamous cells gathered from the mid-vaginal walls by a swipe of a cotton-tipped applicator. Cells indicative of normal maturation include a preponderance of mature superficial squames rather than intermediate or basal cells. Another indicator of a non-atrophic vaginal milieu is a pH under 5.0 as judged by color change on litmus paper. In the absence of confounding vulvovaginal conditions, these clinical tests assess vaginal atrophy. There is not a similar test for atrophy of the vulvar vestibule, and it is assessed visually and assumed to be atrophic when vaginal atrophy is present.

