 - iv. A history of peak menopausal symptoms >2 year prior in women age>51 with no functioning uterus (previous ablation or hysterectomy)
 - v. FSH >40 in women of age >51 if they have no prior history of classic menopausal symptoms (hot flashes, night sweats) and have 1 ovary but amenorrhea that was surgically induced (by ablation or hysterectomy)
- 3. Onset of dyspareunia after menopause but not before.*
- 4. Stable heterosexual partnership ≥1 years (or by investigator discretion if less than 1 years) and both partners want to have more satisfying penetrative intimacy.
- 5. No estrogen product use, local or systemic, for 6 months.
- 6. More than 6 months of consistent insertional pain with intercourse (may have stopped having intercourse due to this consistent experience of pain).*
- 7. Willingness to enter a study where she will receive low-dose local estrogen.*
- 8. Willingness to enter a study that requires application of cream on a frequent schedule for 3 months. *
- 9. Willingness to evaluate the progress of therapies by use of the Tampon Test as many as 2 times per week, and willingness to attempt intercourse if the Tampon Test indicates tolerable penetrative pain.*

Exclusion Criteria

- 1. Consistently has pain in the pelvis or low abdomen (chronic pelvic pain)
- 2. Negative cotton-swab touch test in the vulvar vestibule* or vestibular tenderness that is not extinguishable by application of lidocaine 4% topical solution applied for 3 minutes.
- 3. Partner with sexual dysfunction limiting his performance or making it inconsistent. (The use of male therapy for erectile dysfunction is acceptable.)
- 4. Diagnosis by a physical therapist or clinician of significant pelvic floor muscle tension causing pain (pelvic floor myalgia) or has been found on screening examination to have pelvic floor tenderness or bladder tenderness.
- 5. Constant burning pain localized to the vulva.
- 6. Allergy to local estrogen products or lidocaine numbing agents.*
- 7. Previous estrogen receptor positive breast cancer or endometrial cancer or has been cautioned about estrogen because of any other cancer
- 8. Endometrial thickness ≥5mm on screening via transvaginal ultrasound.
- 9. Vulvovaginitis assessed at screening exam.

^{*}n/a for reference group

^{*}n/a for reference group

Vulnerable Populations

This study will not include special populations. The criteria for the intended population will exclude groups designated as special populations.

Setting

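### The biopsy sub-study is sized, and its only histology test named, on a yes/no inflammation grade instead of the density and nerve changes of primary endpoint 3, and its 80% power does not hold for an exact test

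*Combined protocol and SAP*

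**What the plan says.** Primary endpoint 3 in section 2 reads "Changes in tissue lymphocyte densities and neuronal hyperplasia comparing baseline to study end". Section 3 gives the reason for the nerve measure. It states that "postmenopausal dyspareunia is a localized pain condition of the vestibule and is caused by neural hyperplasia", and it plans before-and-after biopsies "comparing neural hyperplasia, lymphocyte and mast cell infiltrate densities, which are all hallmarks of localized provoked vestibulodynia".

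Section 12 has one histology power statement. It covers 20 women, 10 per arm and pooled, with a one-sided exact test at alpha 0.05 and 80% power to "detect a difference of 15.6% in inflammation, assuming the baseline proportion of moderate or strong inflammation is 95" per cent. It then says that each woman's 3-month biopsy will be compared with her baseline biopsy, without naming a variable, test or estimate. In section 12, neural hyperplasia appears only in what is expected of the five reference women.

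The 95% is credited to the research group's earlier histology series. Section 3 describes the postmenopausal women in that work as those "who still had dyspareunia despite use of systemic and/or local vaginal estrogens". Inclusion criterion 5 of this trial requires "No estrogen product use, local or systemic, for 6 months". Section 5 replaces women without a second biopsy until 20 pairs exist, so 20 is the analysed number.

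**The concern.** The variable used for sizing is not the endpoint. A yes/no grade with 95% of women above the cut at baseline registers a change only when a woman crosses that cut, so a fall from strong to moderate counts as none. The mechanism on which hypothesis 2 and primary goal 4 rest, neural hyperplasia, has no stated analysis or sensitivity.

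Two things are at stake. First, the investigators may think that 20 pairs are adequate for endpoint 3 when the only calculation concerns something else and is too favourable for an exact test. Second, with several markers, possible scales and no named test, the analysis would be chosen after the data are seen. That invites selective reporting of a primary endpoint.

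**Working it through.** **Inputs from section 12.** n = 20; one-sided alpha 0.05; baseline 0.95; fall 0.156, so the target is 0.794. The section does not say whether the test has one sample or two. That is inferred here from which calculation returns the stated figure.

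**Step 1: reproduce the 80%.** One-sample normal approximation against a fixed 0.95:
- SE under the null = √(0.95 × 0.05 / 20) = 0.0487
- SE under the alternative = √(0.794 × 0.206 / 20) = 0.0904
- Power = Φ[(0.156 − 1.645 × 0.0487) / 0.0904] = Φ(0.84) = 79.9%
- Detectable fall at 80% power = 15.63 points

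This matches both stated figures. Other variants do not: arcsine gives 70.9%, Fisher 20 v 20 gives 23.2%, and Fisher 10 v 10 gives 8.1%.

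**Step 2: apply an exact one-sample test.** X is the number of 20 women with moderate or strong inflammation.

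| Reject if | True alpha, P(X ≤ c given 0.95) | Power, P(X ≤ c given 0.794) |
|---|---|---|
| X ≤ 16 | 0.016 | 61.4% |
| X ≤ 17 | 0.075 | 81.2% |

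Only the first row keeps alpha at or below 0.05. With it, 80% power needs a true rate of 74.1%, which is a fall of 95 − 74.1 = 20.9 points.

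**Step 3: treat 95% as uncertain.** Suppose that treatment does nothing and the true rate is below 95%. The chance that the same test declares a fall is P(X ≤ 16): 35% if the rate is 85%, and 59% if it is 80%. These rates are assumptions chosen to show sensitivity.

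**Step 4: compare the paired grade with a paired continuous score.** The documents give no SD, no within-woman correlation and no rule linking grade to density. Assume a normal latent score with equal SD at both visits, with the grade as a cut on it. Then:
- Shift = z(0.95) − z(0.794) = 1.645 − 0.820 = 0.82 SD
- Standardised paired change = 0.824 / √(2(1 − ρ))
- Exact McNemar: reject when P(Bin(b + c, ½) ≥ b) ≤ 0.05, where b women leave the category and c enter it. At ρ = 0.5 the cell probabilities are 0.176 and 0.020.

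| ρ | Paired change (SD of differences) | McNemar, one-sided | Signed-rank, one-sided (simulated) | Paired t, one-sided |
|---|---|---|---|---|
| 0 | 0.58 | 20% | 79% | 81% |
| 0.3 | 0.70 | 20% | 90% | 91% |
| 0.5 | 0.82 | 20% | 96% | 97% |
| 0.7 | 1.06 | 20% | 99.8% | 99.8% |

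**Step 5: sensitivity of 20 pairs on a continuous measure.** At 80% power and two-sided 5%, the detectable change is 0.66 SD of the paired differences (paired t, noncentral t) or 0.68 SD (signed-rank). If alpha is split equally between two measures (two-sided 2.5% each), the paired t figure becomes 0.74 SD.

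**The case against.** The strongest reply is that a sizing sentence is not an analysis plan. Sections 2 and 3 plan a before-and-after comparison of neural hyperplasia and of densities, and section 12 compares each woman with herself. This stands. A reader might infer that the mechanism goes untested or that the density data will be thrown away. The documents do not support that: nothing says that the biopsies will be analysed only as a grade. What is missing is a named test and a statement of power.

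A second reply concerns the 20%. McNemar's test appears nowhere in the plan, so a claim that the plan discards most of its power goes too far. Under the plan's apparent one-sample framing, the exact power is 61%. The comparison also treats the grade as a cut on the density, while the point here is that the two variables differ. Step 4 is therefore an illustration of what a threshold costs, not an estimate for this trial.

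Third, 95% might be called a ceiling. It is not one here, because the expected change is downward and the scale has room. The difficulty is an extreme cut-point.

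Fourth, one clause in section 3 does not show that women off estrogen have a different rate, or in which direction. The most that can be said is that 95% may not transfer.

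Finally, this is a pilot. That excuses a small sample, but it does not remove the need for a stated analysis of a primary endpoint.

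**Conclusion.** The mismatch is clear from the text: sizing and the only named histology test use an inflammation proportion, while primary endpoint 3 is a paired change in lymphocyte density and neuronal hyperplasia with no test or power given.

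The arithmetic finding is also firm, given the one-sample reading that reproduces the plan's figures. The power is 61% by the exact test, not 80%, and about 21 points are needed, not 15.6. The 35% false-positive figure is conditional on a true baseline of 85%. The contrast of about 20% with 79% to 99.8% is conditional on the paired grade being the analysis, on the latent-normal link and on a correlation of 0 to 0.7.

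The documents do not support a conclusion that neural hyperplasia goes unmeasured, or that the sub-study cannot answer its question. The same 20 pairs can answer it if the analysis is named. The change should be made, but it does not invalidate the design.

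**What to change.** In section 12:

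1. Define endpoint 3 as each woman's month-3 minus baseline lymphocyte density and nerve measure.
2. Test each with a paired signed-rank test, using an exact method that handles ties if a measure is ordinal, and report an estimate of change with a 95% CI.
3. State the order of the two tests, or split alpha. Say whether the mast cell density named in section 3 is supportive.
4. Report the moderate/strong proportion descriptively, against the women's own baseline and not against 95%.
5. Replace the 80%/15.6-point statement with the detectable change for 20 pairs: about 0.66 to 0.68 SD of the paired differences at 80% power, two-sided 5%, and somewhat larger if alpha is split.

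No extra women, visits or biopsies are needed. Section 11 says only that specimens will be stained and analysed, so the counting or grading method should be written down first; that may add a little work for pathology. The downside is that the stated sensitivity changes and the two tests need an order.
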